Univariate and multiple logistic regression (MLR) methods will be used to investigate the impact of various explanatory covariates (e.g. demographic and disease characteristics, co-morbidities, type of treating institution, and prior treatment for CHC and response outcome in treatment experienced patients) on SVR12. These analyses will be of exploratory nature, data driven, and will be performed for various CP analysis groups since not each covariate might be predictive in each patient group. Furthermore, the fact that treatment regimens will differ in the various patient groups has to be taken into account, when selecting the patient groups for each MLR analysis. Backward selection procedures will be applied to generate the final MLR models which will consider only covariates in the selection procedure with a p-value <0.25 in the corresponding univariate logistic regression analysis. A p-value <0.05 will be used for the covariates to stay in the model in a backward elimination step. Logistic regression methods will also be used to investigate the impact of treatment adherence on SVR12.

All safety variables will be summarized for patients in the SP using descriptive statistical methods stratified by the type of combination treatment and scheduled treatment duration.

Milestones:

Start of Data Collection:	October 2015
End of Data Collection for Interim Analysis:	December 2016
End of Data Collection for Final Report:	March 2017
Interim Analysis of Study Results:	March 2017
Final Report of Study Results:	June 2017

Confidential Information

No use or disclose outside AbbVie is permitted without prior written authorization from AbbVie

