9.7.2 Demographics and Disease Characteristics

All baseline and disease characteristics will be summarized for the CP stratified by the CP analysis groups (i.e. based on genotype 1 subtype, fibrosis status, treatment experienced or naïve), which are relevant for scheduled treatment combination

Confidential Information

No use or disclose outside AbbVie is permitted without prior written authorization from AbbVie

(ABBVIE REGIMEN ± RBV) and duration (12 and 24 weeks). In addition, baseline summaries will be repeated for the SP and the TP without stratification into subgroups. Summary statistics (n, mean, median, standard deviation [SD], and range) will be generated for continuous variables (e.g. age and body mass index [BMI]). The number and percentage of patients will be presented for categorical variables (e.g. gender and race). Further details of analysis populations and the CP analysis groups will be specified in the SAP, taking into account the ABBVIE REGIMEN recommended in the current local label for various patient groups.

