9.7.6 Tolerability Analysis

All tolerability variables will be summarized using descriptive statistical methods for the SP stratified by type of combination treatment and scheduled treatment duration.

All SAEs, non-serious AEs and pregnancy occurrences are to be reported for patients included in the study (see Section 11.0 and 9.2.3). AEs will be coded using MedDRA. The number and percentage of patients with treatment-emergent AEs (i.e. any reported event that begins or worsens in severity after initiation of study drug through 30 days post-study drug dosing) will be tabulated by primary MedDRA SOC and PT. Corresponding summary tables will be provided for all serious treatment-emergent AEs. The tabulation of the number of patients with treatment-emergent AEs by severity and relationship to study drug will also be provided. Patients reporting more than one AE for a given MedDRA PT will be counted only once for that term using the most severe incident for the severity summary table and the most related for the relationship summary table. Patients reporting more than one type of event within a SOC will be counted only once for that SOC.

Additional details of the analysis of AEs will be specified in the SAP.

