#### SP analysis groups

The SP analysis groups are defined according to the treatment regimen and patient's fibrosis status. The standard summaries by SP groups in the safety population are as follows (if not specified otherwise):

- Total (regardless of cirrhosis status)
  - (1) Total
  - (2) 2DAA w/o RBV
  - (3) 2DAA + RBV
  - (4) 3DAA w/o RBV
  - (5) 3DAA + RBV
- Patients with cirrhosis
  - (6) Total
  - (7) 2DAA w/o RBV
  - (8) 2DAA + RBV
  - (9) 3DAA w/o RBV
  - (10) 3DAA + RBV
- Patients without cirrhosis
  - (11) Total
  - (12) 2DAA w/o RBV
  - (13) 2DAA + RBV
  - (14) 3DAA w/o RBV
  - (15) 3DAA + RBV
- · Patients with unknown fibrosis status
  - (16) Total
  - (17) 2DAA w/o RBV
  - (18) 2DAA + RBV
  - (19) 3DAA w/o RBV
  - (20) 3DAA + RBV

(2DAA - paritaprevir/r-ombitasvir, 3 DAA - paritaprevir/r-ombitasvir + dasabuvir, RBV – ribavirin taken, w/o RBV – no ribavirin taken)

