# 4.2.7 Analyses of the Objectives

#### 4.2.7.1 Primary Effectiveness Variable

The primary objective of this study is to estimate the SVR12 rates in HCV patients treated according to the ABBVIE Regimen.

Therefore the simple percentage of patients achieving SVR12 (for definition see section 4.1.1) will be calculated and a two-sided 95% confidence interval (CI) of the percentage will be computed based on the Wilson's Score method.

The primary effectiveness analysis on clinical outcomes will be performed on all patients in the CP stratified by genotype and cirrhosis status and overall.

In the framework of sensitivity analyses the primary analyses will be repeated for the CPSFU . Furthermore, the SVR12 rates will be also determined for all patients of the NCP.

An overview of Tables is given in Table 8.

The layouts of the tables mentioned above are provided in Part II of the SAP (Table Shells).

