## 4.2.8 Analyses of Safety

All safety variables will be summarized for patients in the SP using descriptive statistical methods stratified by treatment regimen and cirrhosis status and overall.

An overview of tables for the individual values is given in Table 12.

The layouts of the tables mentioned above are provided in Part II of the SAP (Table Shells).

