#### 4.2.8.3 Adverse Events

All tolerability variables will be summarized using descriptive statistical methods for the SP stratified by treatment regimen and cirrhosis status and overall.

AEs will be coded using MedDRA. A glossary will show the verbatim terms and the corresponding coded terms used (see Table 12).

The number and percentage of patients with treatment-emergent AEs (i.e. any reported event that begins or worsens in severity after initiation of study drug through 30 days post-study drug dosing including those who are related to the study drug independent of the occurrence and those where the date of onset is missing) will be tabulated by primary MedDRA SOC and PT.

Corresponding summary tables will be provided for all serious treatment-emergent AEs and additional for all non-serious treatment-emergent AEs. In the table of non-serious AEs (that must exclude any SAE) only preferred terms that occurred at a frequency of >=5% in any treatment group will be displayed (no SOCs will be displayed).

The tabulation of the number of patients with treatment-emergent AEs by severity (AEs by severity [mild, moderate, severe], AEs leading to death, AEs leading to hospitalization) and relationship to study drug will also be provided (ABBVIE Regimen, ribavirin, medication error – paritaprevir/r-ombitasvir, medication error – dasabuvir, ABBVIE Regimen withdrawn, ribavirin withdrawn).

Patients reporting more than one AE for a given MedDRA PT will be counted only once for that term using the most severe incident for the severity summary table and the most related for the relationship summary table. Patients reporting more than one type of event within a SOC will be counted only once for that SOC.

The frequency of pregnancies will be displayed as well.

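### The SAP replaces scheduled treatment duration with cirrhosis status as a stratum for the tolerability tables, undeclared, and no listed output gives AEs by planned 12 versus 24 weeks

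*SAP*

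**What the plan says.** **Tolerability.** Protocol 9.7.6 has all tolerability variables summarised for the safety population "stratified by type of combination treatment and scheduled treatment duration". The Data Analysis part of the protocol abstract repeats the rule: "stratified by the type of combination treatment and scheduled treatment duration". What 9.7.6 hands over is narrower: "Additional details of the analysis of AEs will be specified in the SAP".

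The SAP sets different strata. In 4.2.1, "The SP analysis groups are defined according to the treatment regimen and" the patient's fibrosis status. The 20 resulting groups cross 2DAA or 3DAA, with or without RBV, with cirrhosis status, and have no 12/24-week level. SAP 4.2.8 then has all safety variables summarised "stratified by treatment regimen and cirrhosis status and overall", and 4.2.8.3 does the same for adverse events. An event counts as treatment-emergent from first dose "through 30 days post-study drug dosing". The SAP also counts drug-related events whenever they occur and events with no onset date.

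**SVR12.** Protocol 9.7.2 describes the CP analysis groups as "based on genotype 1 subtype, fibrosis status, treatment experienced" or naive, and Protocol 9.7.3 stratifies the primary analysis by those groups. The SAP groups use genotype/subtype and fibrosis status only. Under SAP 4.2.7.1 the primary analysis "will be performed on all patients in the CP stratified by genotype and cirrhosis status and overall".

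**The concern.** Tolerability is a stated secondary objective, and the protocol fixed scheduled duration as one of its two strata. A patient planned for 24 weeks is watched for treatment-emergent events for much longer than one planned for 12. A row that pools the two gives an AE percentage that depends on the duration mix as well as on tolerability. If 24-week patients fall mainly in one regimen row, part of any difference between regimen rows could be observation time.

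The SAP does declare other departures: 4.1.1 explains the 126-day upper bound for SVR12, and 4.2.8.4 says that laboratory shift tables are replaced. A reader would reasonably assume that strata not mentioned still follow the protocol.

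**Working it through.** **Step 1: does cirrhosis status stand in for duration?** Only in part. The exploratory regression text in SAP 4.2.7.2.1 gives cirrhotic G1 patients as a subgroup in which 12 and 24 weeks might be compared, so the SAP expects both durations within one cirrhosis stratum. Protocol 7.1 likewise describes a cirrhosis study with 12- and 24-week arms on the same combination with RBV. Mixing is therefore most likely in the cirrhotic 3DAA + RBV row and in the total rows that contain it.

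**Step 2: does a listed output restore the split?**

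| Place in SAP | What it gives | Why it is not the protocol's split |
|---|---|---|
| Table 12, AE summary tables | AEs by regimen and cirrhosis status | No planned duration |
| 4.2.8.1, exposure | Actual duration by regimen and cirrhosis status | No AEs by duration |
| 4.2.9, interim | All analyses in patients planned for 12 weeks who started before 1 April 2016 | Interim only; no 24-week rows |
| 4.2.7.2.1, optional subgroup regression | 12 vs 24 weeks on SVR24 | Not AEs; conditional |

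**Step 3: length of the treatment-emergent window.** The plan gives no AE rate or duration mix to reproduce. The windows follow from its definitions:
- 12 weeks: 84 + 30 = 114 days
- 24 weeks: 168 + 30 = 198 days
- ratio: 198 / 114 = 1.74

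**Step 4: what equal tolerability would look like.** Let p be the proportion with any AE over a 12-week course. The documents give no value, so 30-70% is assumed. If all events occur early, the 24-week proportion is also p. Under an assumed constant hazard it is 1 - (1 - p)^1.737:

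| p (12 weeks) | 24 weeks | Difference |
|---|---|---|
| 30% | 46.2% | +16.2 points |
| 50% | 70.0% | +20.0 points |
| 70% | 87.6% | +17.6 points |

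**Step 5: effect on a mixed row.** If a share f of the row is on 24 weeks, the row lies f x difference above its own 12-week rate. The share is not in the documents; 10-50% is assumed.
- f = 10%: 0.10 x 16.2 to 0.10 x 20.0 = 1.6 to 2.0 points
- f = 50%: 0.50 x 16.2 to 0.50 x 20.0 = 8.1 to 10.0 points
- all events early: 0 points for any f

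**Step 6: the SVR12 stratum.** Protocol Table 1 (non-cirrhotic, with RBV) gives, naive minus experienced:
- genotype 1a: 95 - 96 = -1 to 97 - 96 = +1 point
- genotype 1b: 98 - 97 = +1 to 99.5 - 97 = +2.5 points

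The 1b pair without RBV gives 99 - 100 = -1. These are contrasts across studies, and the documents give no direct naive versus experienced figure in cirrhosis.

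For precision, assume that 20-50% of 360-380 CP patients are experienced. That is 0.2 x 360 = 72 to 0.5 x 380 = 190 experienced, and 0.5 x 360 = 180 to 0.8 x 380 = 304 naive. Widths of the Wilson 95% interval, the SAP's method:

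| SVR12 | Experienced, n = 72 / 190 | Naive, n = 180 / 304 |
|---|---|---|
| about 90% | 13.9 / 8.6 points | 8.8 / 6.7 points |
| about 95% | 11.3 / 6.5 points | 6.6 / 5.0 points |

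Contrasts of this size could not be resolved, so the split would be descriptive only.

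**The case against.** **The upper figure rests on assumptions.** The AE risk, the constant hazard and the share on 24 weeks are all assumed. Protocol 7.1 points towards the low end: many AEs are attributed to RBV, a stratum the SAP keeps, and bilirubin elevations peaked by Week 1. Its cirrhosis results suggest that the longer course matters for one subgroup, so half of a total row on 24 weeks is unlikely. This stands. A reader might infer that the AE tables will be wrong by 10 points; the documents do not support that.

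**Other outputs help.** The exposure table shows the duration behind each regimen-by-cirrhosis row. With inclusion planned for about six months from October 2015, the interim could cover most 12-week patients unmixed, although the increase to 400 patients may have lengthened recruitment. Both soften the point, but neither gives AEs by planned duration in the final analysis.

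**The table shells are unseen.** Absence is judged from the SAP text and output titles. The mismatch in strata is certain; that no final table shows the split is certain only for the listed outputs.

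**The SVR12 groups were largely delegated.** Protocol 9.7.2 leaves further detail of the CP groups to the SAP in light of the local label, and SAP 4.2.1 ties the label to cirrhotic status and genotype. Prior treatment also remains a covariate in the SVR24 model. This largely stands. What remains is that 9.7.2 itself names naive/experienced as a basis, and the SAP does not say why it was dropped. A reader might infer that the primary analysis is compromised; it is not, because the overall CP estimate does not depend on these strata.

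**Conclusion.** The point holds for tolerability. The protocol fixed scheduled duration as a stratum and left only additional detail to the SAP. The SAP substitutes cirrhosis status without saying so, and no listed output restores the split. Cirrhosis status is an incomplete substitute, because both durations are expected among cirrhotic G1 patients.

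The 114- versus 198-day windows follow directly from the definitions. The resulting distortion is unknown: zero if events occur early, and up to about 10 points in a mixed row under a constant hazard, a 12-week AE risk of 30-70% and up to half the row on 24 weeks. The case for change is that a protocol analysis is missing and mixed rows are hard to interpret, not that a bias has been shown.

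The SVR12 stratum is secondary and minor: an unexplained change, small contrasts outside cirrhosis on the documents' own figures (-1 to +2.5 points), and no effect on the overall estimate.

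**What to change.** **Main change (SAP 4.2.8, 4.2.8.3 and Table 12).** Keep the regimen-by-cirrhosis tables. Add two outputs for the safety population, by regimen and planned duration (12 versus 24 weeks): treatment-emergent AEs and serious treatment-emergent AEs. Use planned duration, as the protocol states; actual duration is itself shortened when an AE ends treatment. State in 4.2.8 that cirrhosis status was added as a stratum, and why. If the sponsor decides to keep only the SAP strata, declare the departure with its reason, as 4.1.1 and 4.2.8.4 do for other changes.

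**Secondary change (SAP 4.2.1 or 4.2.7.1).** Add a sentence noting that naive/experienced status is no longer a basis of the CP analysis groups, with the reason. One descriptive SVR12 table for the CP by naive versus experienced is optional.

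**Cost.** A few descriptive tables from data already collected. Planned duration is already used in the adherence formula and the interim restriction, and pre-treatment status in the regimen tables of SAP Table 6. Some cells will be small, so the tables should be labelled descriptive.

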# 4.2.7.2 Secondary Variables

# 4.2.7.2.1 Secondary Effectiveness Variables

#### Response

For the other response rates (i.e. RVR, SVR24, EoT response rate, relapse rate, viral breakthrough), the simple percentage of patients and a two-sided 95% confidence interval (CI) of the percentage will be computed (based on the Wilson's score method) as well. The RVR and EoT response rates will be reported for CP and the SVR24 rate will be reported for the respective CPSFU, stratified by genotype and cirrhosis status and overall. The relapse rates will be estimated stratified by SVR window (i.e. during SVR12 window=relapse12, during SVR24

window=relapse24) and stratified by genotype and cirrhosis status and overall in patients of the CP with EoT response who fulfilled the following criteria:

- completed treatment as defined previously.
- had at least one HCV RNA measurement >= 70 days post-treatment or was a treatment failure between EoT and 70 days post-treatment.

Viral breakthrough rates [defined as at least one documented HCV RNA <50 IU/mL followed by HCV RNA ≥50 IU/mL during treatment] will be estimated overall and stratified by genotype and cirrhosis status in all patients of the CP, who have at least one undetectable or unquantifiable, ontreatment HCV RNA measurement and at least one on-treatment or EoT measurement thereafter.

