## Core Population with Sufficient Follow-up [CPSFU {12, 24}]

In addition, the core population with sufficient follow-up data regarding SVR12 or SVR24, respectively, is defined as all CP patients,

- who have evaluable HCV RNA data ≥70 days or >126 days, respectively, after the last actual dose of the ABBVIE REGIMEN
- or a HCV RNA value ≥50 IU/mL at the last measurement
- or had HCV RNA <50 IU/mL at the last measurement, but no HCV RNA measurement ≥70 days or >126 days, respectively, after the last actual dose of the ABBVIE REGIMEN due to reasons related to safety (e.g. dropped out due to adverse event) or virologic failure (e.g. virologic failure such as relapse is reported in the electronic case report form (eCRF) but date and value of the corresponding HCV RNA test is missing).

This means only patients who had virological response at their last on-treatment or post-treatment measurement, but had no HCV RNA measurements ≥70 days or >126 days, respectively, post-treatment for reasons not related to safety or effectiveness (e.g. lost-to-follow-up or patient not willing to perform an additional HCV RNA test ≥70 days or >126 days, respectively, post-treatment) will be excluded from this analysis.

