**Table 2 - Data Documentation Schedule** 

Assessment/ Procedure		Treatment Period		Post-treatment (PT) Period			
(only available data to be collected; no diagnostic or monitoring procedures to be applied to the patients apart from those of routine clinical practice)	Baselin	On- treatment visits	Mid treatment visit for pts receiving 24 weeks of therapy	EoT b	Early PT visit	SVR 12 visit	SVR 24 visit
Patient authorization	X a						
Demographic information	Χ						
IL28B	Χ						
Relevant CHC disease characteristics	Х						
Liver fibrosis stage	Х						
CHC treatment history	Χ						
HCV genotype and subtype	Χ						
HCV RNA samples	Х	Х	Х	Х	Х	Χ	Χ
Clinical chemistry and hematology	Χ	Х	Χ	Х	Х	Х	Х
ABBVIE REGIMEN initiation documentation	Х						
ABBVIE REGIMEN adherence		Х	Χ	Х			
Concomitant medication	Χ	Х	Χ	Χ			
Relevant medical history, co-morbidities	Χ						
sAE, AE and pregnancy reporting	Х	Х	Х	Х	Xc	$X_q$	Xd
For patients receiving RBV: Evidence, in accordance with local label, that female patient or female partner of male patient is not pregnant	Х						
Patient questionnaires – WPAI, EQ5D-5L	Χ			Х		X	Х

Abbreviations: EoT = End of Treatment (at Week 12 or 24 or at premature discontinuation), PT = Post-Treatment

- a Written patient authorization must be obtained before any data documentation in the eCRF
- b Patients who prematurely discontinue should return to the site to document EoT data
- c Tolerability documentation until PT week 4
- d Pregnancy reporting for patients treated with DAA plus RBV

In accordance with the non-interventional nature of the study all HCV RNA measurements will be performed at the sole discretion of the physician and all HCV RNA measurements have to be entered into the eCRF. All recorded HCV RNA values will be assigned to appropriate time points (baseline, on-treatment visits, EoT visit, post-treatment visits) as follows:

Table 3 - Analysis Time Windows for HCV RNA

Phase	Time point	Time Window
Pre-Treatment	Baseline	Last value prior to start of study treatment (i.e.
		≤study day 1)
On-treatment		Study day during treatment period^#
		(Study day 1 = first treatment day)
Treatment Week	4 (RVR*)	15 - 42^
EoT	Actual EoT	Study day of last dose#
		(28 days prior to last dose - 7 days post last
		dose)
Post Treatment	12 weeks (SVR 12	>=70-126 days post last dose
	window)	
	24 weeks (SVR24	127-210 days post last dose
	window)	

^values must also be <= 7 days post last dose

#>=study day 2

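### SVR24 is reported in a population that keeps failures known by day 126 but drops responders not retested later, so it is biased low if late tests are missed at random

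*SAP*

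**What the plan says.** SAP 4.2.7.2.1 (Response) assigns RVR and EoT response to CP, but for the latest time point it states that "the SVR24 rate will be reported for the respective CPSFU". SAP 4.2.1 gives a CP patient three ways into CPSFU24:

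1. A late value: patients "who have evaluable HCV RNA data ≥70 days or >126 days, respectively, after the last actual dose of the ABBVIE REGIMEN" (for SVR24 the second limit applies).
2. A failure: "or a HCV RNA value ≥50 IU/mL at the last measurement", with no condition on when that measurement was taken.
3. A response at the last test and no late test, where the late test is missing "due to reasons related to safety (e.g. dropped out due to adverse event) or virologic failure".

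The remaining patients, who were responders at their last test and have no late value "for reasons not related to safety or effectiveness (e.g. lost-to-follow-up or patient not willing to perform an additional HCV RNA test", "will be excluded from this analysis".

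SAP 4.2.2 sets the SVR24 window at "127-210 days post last dose" (Table 3) and notes that "all HCV RNA measurements will be performed at the sole discretion of the physician". Under SAP 4.2.3 a value after the window can be carried back into it, and a value that is still missing counts as failure. The primary SVR12 analysis is in CP under that rule and is repeated in CPSFU (SAP 4.2.7.1). Relapse is tabulated separately for the SVR12 and SVR24 windows. Its denominator is CP completers with EoT response who have either a test at least 70 days post-treatment or an earlier failure.

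**The concern.** Entry to CPSFU24 depends on the outcome. A patient known to have failed by day 126 is always counted. A patient in response at that point is counted only if someone orders another test, apart from those missing for safety or failure reasons. This selection lowers the rate even when missed late tests have nothing to do with prognosis, and a larger sample does not remove it. The imputation rules do not help: flanking and carry-back both need a value after the window, so a responder with no test after day 126 cannot be recovered.

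Readers will set SVR12 and SVR24 side by side. If SVR24 is lower because of who was retested, the difference could be taken as loss of response between weeks 12 and 24. The same mechanism stretches contrasts between the genotype and cirrhosis strata in which SVR24 is reported.

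**Working it through.** **The plan's own figure.** SAP Table 1 concerns SVR12 only. Exact Clopper-Pearson limits at N = 360 are 86.4 to 92.9 for 324/360 (width 6.5) and 92.2 to 97.0 for 342/360 (width 4.8), as printed. No planning figure is given for SVR24 or for missing week-24 tests.

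**Inputs.**
- S, the true SVR24 rate: 95% or 90%. These are the planning rates for SVR12 (SAP 3.2); using them for SVR24 is an assumption.
- E, the share failing and known by day 126; L, the share whose failure can be detected only later; S + E + L = 1.
- r, the share of patients not yet failed who are retested after day 126: assumed, 50 to 90%, because the documents give none.

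**Expected rate in CPSFU24 when late tests are missed at random:** S·r / (S·r + E + L·r). With L = 0 the odds of response are multiplied by r.

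| Retested r | True 95% | Bias | True 90% | Bias |
|---|---|---|---|---|
| 90% | 0.855/0.905 = 94.5% | -0.5 | 0.81/0.91 = 89.0% | -1.0 |
| 80% | 0.76/0.81 = 93.8% | -1.2 | 0.72/0.82 = 87.8% | -2.2 |
| 70% | 0.665/0.715 = 93.0% | -2.0 | 0.63/0.73 = 86.3% | -3.7 |
| 50% | 0.475/0.525 = 90.5% | -4.5 | 0.45/0.55 = 81.8% | -8.2 |

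A simulation at N = 360, S = 95%, r = 70% gave a mean of 93.0%.

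**Late failures.** With S = 95%, r = 70% and half the failures late, the rate is 0.665/(0.665 + 0.025 + 0.0175) = 94.0%. If all failures are late (E = 0), r cancels and the bias is zero.

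**Scale.** A bias compares with a half-width. From SAP Table 1 at N = 360 these are 4.8/2 = 2.4 points at 95% and 6.5/2 = 3.25 points at 90%.

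**Strata.** At r = 70%, true rates of 95% and 90% are reported as 93.0% and 86.3%, so a 5-point gap becomes 6.7.

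**Against SVR12, with no late relapse.** Take a true 95% at both times, 5% of responders missing at week 12 and 30% at week 24.
- SVR12 in CPSFU12: 0.9025/0.9525 = 94.8%.
- SVR12 in CP, missing = failure: 0.95 × 0.95 = 90.3%.
- SVR24 in CPSFU24: 93.0%.

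The result is a false fall of 1.7 points from CPSFU12 but a rise of 2.8 points from the primary CP rate. SVR24 drops below the CP rate only when more than about 29% (2% missing at week 12) or 51% (5% missing) of responders lack a late test.

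**Relapse24.** Its denominator admits patients whose last test fell between days 70 and 126, and they cannot show late relapse. If 1% relapse late and 70% are retested, about 0.01 × 0.7 = 0.7% is seen. Relapse24 therefore tends to be understated while SVR24 is biased low.

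**Alternative estimator.** Multiply the share of CP without failure by day 126 by the share still below 50 IU/mL among those non-failures who were retested. With 4% early failure, 1% late relapse and r = 70%: 0.96 × (1 − 0.01/0.96) = 95.0%, the true value; simulation agreed at 95.0%. CPSFU24 would give 0.665/(0.665 + 0.04 + 0.007) = 93.4%. Moving SVR24 to CP with missing = failure would be worse: 0.95 × 0.7 = 66.5%.

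**The case against.** The strongest case against is that the consequence is limited. SVR24 is a descriptive secondary rate that the SAP adds (4.1.2). It is not among the effectiveness endpoints in Protocol 9.7.3.2, and no decision rests on it. The visit schedule includes an SVR24 test and is said to reflect anticipated regular follow-up. If 90% of responders are retested, the bias is only 0.5 to 1 point. Protocol 9.9 already warns that missing HCV RNA can understate SVR. SAP 4.2.5 already tabulates population membership and reasons for exclusion, and relapse24 is reported on its own. All of this is correct and keeps the point moderate. It does not remove it: the direction of the bias is built into the definition, no sensitivity analysis is planned for SVR24, and relapse24 includes patients with no late test.

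A reader might infer three stronger things that the documents do not support.

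- That the report will show a drop resembling late relapse. The headline SVR12 rate is in CP with missing = failure, and SVR24 can sit above it. A false fall arises mainly against CPSFU12, and it is then the difference of two biases of the same kind.
- That cured patients in routine care usually skip the late test. The documents leave testing to the physician and give no retest share.
- That the CPSFU24 rate is a lower bound. If late relapsers are retested less often than responders, it can be too high. With 5% late failures of whom 50% are retested, and 90% of responders retested (assumed), it is 0.855/(0.855 + 0.025) = 97.2% against a true 95%.

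**Conclusion.** The concern holds in this form: if late tests are missed at random, SVR24 in CPSFU24 is biased low unless every failure appears after day 126. With all failures known by day 126, the expected bias is 0.5 to 1.0 point at 90% retested, 2.0 to 3.7 points at 70% and 4.5 to 8.2 points at 50%, for true rates of 95% and 90% respectively. It shrinks as more failures occur late. Patients missing for safety reasons who enter by the third route without a late value count as failures and lower the rate further. The size rests on retest shares that the documents do not give. A fall from SVR12 in CPSFU12 to SVR24 in CPSFU24 could be misread as late relapse; a comparison with the primary CP rate may point the other way. Relapse24 does not settle which reading is right. The change is worth making, but the primary analysis is not affected.

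**What to change.** Add to the response table:

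- (a) Among patients with an observed (not imputed) HCV RNA below 50 IU/mL in the 70 to 126 day window and a value after day 126, the percentage still below 50 IU/mL, with its CI. Imputed SVR12 values must be left out. SAP 4.2.3 lets a later value fill that window, so a patient could be called an SVR12 responder because of the very test used to judge durability.
- (b) As a supplementary SVR24 estimate, the share of CP without failure by day 126 times the share still below 50 IU/mL among those non-failures retested after day 126. State the assumption that untested patients behave like tested ones. The first factor should not be SVR12 in CPSFU12, which carries a smaller version of the same selection.
- (c) The number of responders excluded from CPSFU24 for lack of a late test.

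Add a sentence to the SAP saying that the CPSFU24 rate is biased low if late tests are missing at random, without calling it a lower bound. Another should define failure by day 126, including failures reported without a value and patients missing for safety reasons.

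The cost is a few table rows and these sentences, with no new data. The downside is that (b) rests on a missing-at-random assumption that the study cannot verify.
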